4.10. Participant Operational Definitions

A Screened Participant is one who has signed an ICF. An Enrolled Subject is one who signs the ICF and meets all of the inclusion criteria and none of the exclusion criteria. A Completed Subject is defined as one who has satisfactorily completed all study visits outlined in the protocol. A Usable Dataset is defined as a dataset that meets all of Sponsor's data requirements (i.e., complete study endpoint data from a subject to enable inclusion in the analysis).

5. Study Materials

5.1. Devices

The devices utilized for this study do not meet the definition of a significant risk (SR) device under 21 CFR 812.3(m). Therefore, the study can be classified as a Non-Significant Risk device study:

Does the investigational device meet the definition of an SR device under 21 CFR 812.3(m)?	Yes/No
Is it intended as an implant and presents a potential for serious risk to the health, safety, or welfare of a participant?	No
Is it purported or represented to be for a use in supporting or sustaining human life and presents a potential for serious risk to the health, safety, or welfare of a participant?	No
Is it for a use of substantial importance in diagnosing, curing, mitigating, or treating disease, or otherwise preventing impairment of human health and presents a potential for serious risk to the health, safety, or welfare of a participant?	No
Does it otherwise present a potential for serious risk to the health, safety, or welfare of a participant?	No

5.1.1. Pure Tone Audiometry – [REDACTED] clinical reference system capable of measuring air conduction thresholds in 1 and/or 2.5 dB steps (0.25, 0.5, 1, 2, 3, 4, 6, 8 kHz). Annual calibration on test system required ahead of study start.

5.1.2. Bone Conduction Audiometry – [REDACTED] clinical reference system capable of measuring bone conduction thresholds in 2.5 dB steps (0.5, 1, 2, 4 kHz). Annual calibration on test system required ahead of study start.

5.1.3. Tympanometer [REDACTED] - Diagnostic system capable of performing standard 226 Hz tympanometry. Annual calibration on test system required ahead of study start.

5.1.4. Real Ear measure system

Diagnostic system capable of measuring the frequency-level dependent gain that a given ear receives relative to the acoustic targets defined for a chosen fitting formula (i.e. NAL-NL2 [National Acoustic Laboratories for prescribing nonlinear gain]) This is achieved by placing a probe microphone in the participant's ear canal, after which an expert with headphones in situ will assess the precise level of amplification at every frequency and at different input levels.

5.1.5. Speech-In-Noise (QuickSIN) assessment system

Method of testing a participant's functional hearing ability. The participant's hearing is tested in the presence of background noise.

5.2. Smartphone app

Digital medium through which participants with hearing difficulties will be able to interface with the enabled hearing program.

5.2.1. Self-Tuning in clinic

Hearing aids are fitted by the participants using them. Participants will be randomly sorted into either this group or the Pro-Tuning group.

5.2.2. Pro-Tuning in clinic

Hearing aids are professionally fitted. Participants will be randomly assigned to this group or the Self-Tuning group.

5.2.3. Self-Tuning at home (both groups)

Both groups will be instructed in-clinic on how to modify hearing aid settings to preference during Home Intervals.

5.3. Wireless Headphones

The Sponsor will provide the study site with sufficient quantity of wireless headphones and iPhones to complete the study. Subjects will be instructed to return all equipment at the end of the study.

[figure not shown]
5.4. Device Accountability

Each participant's study device ID number will be recorded in the study database(s). All study equipment will be returned to the Study Staff at the end of the study.

6. Study Assessments

6.1. Figure 1: Diagram of Study Assessments and Procedures

7. Participant Safety

7.1. Anticipated Risks to Participants

Participants may have risks or discomforts while in this study. Precautions will be taken to minimize risks, and the participant will be encouraged to talk to the Study Staff if he/she experiences any injuries, side effects, or discomfort during this study.

Potential risks and discomforts may include:

- **Previously unknown hearing loss:** Participants may experience symptoms of stress and anxiety related to objective finding of hearing loss. They will have access to the study Audiologist who can address frequently asked questions.
- **Discomfort or injury with ear exam and ear wax removal:** Clinic visits include examination of the ears by an audiologist who may remove ear wax if deemed required and consented to by participant. Some participants may experience discomfort with ear exams. Removal of ear wax is

common in audiology practices and considered safe but does have potential risks of eardrum perforation, a laceration in the ear canal, dizziness, and/or inability to remove ear wax.

- **Discomfort with headphone wear:** Some participants may find it uncomfortable to wear the wireless headphones in *Home Interval 1* and in *Home Interval 2*. If comfort prohibits a participant from this wireless headphone wear, they will be withdrawn from the study.
- **Loss of confidentiality due to study data breach:** To minimize this risk, the Study Staff will adhere to rigorous standards to protect the data. All data collected from participants will be coded and separated from any directly identifiable information (DII). Although the Study Staff will take precautions to protect the participant's identity, such as keeping study records in a secure location with restricted access and removing information traditionally used to identify participants when their study data is shared, we cannot guarantee that their identity will never become known to the Study Sponsor. It is possible that there could be unauthorized access to, or security breaches of, the systems used to store information, and there may be other privacy risks that are not foreseen.
- **Loss of confidentiality related to storing health data on an app:** Participants will be reminded not to share their mobile device login information with others and receive training on best practices on preventing the infiltration of DII into the study app. Only the Study Staff will have access to the primary study crosswalk.
- **Provided device configuration changes:** Participants may make changes to the provided smartphone, either intentionally or inadvertently, that compromises the ability of the study software to function properly. The Study Staff will be available to handle usability issues participants experience during the course of their participation. If the Study Staff notice a gap in the data, they may attempt to contact participants to troubleshoot the problem(s).
- **Discomfort associated with being asked personal questions about health history and the completion of questionnaires:** (Infrequent likelihood of risk) Any participant who becomes distressed while completing questionnaires will be encouraged to seek clarification of any questions that he/she find to be unclear or troubling. The participant may skip any question which he/she finds distressing and will be told that he/she do not have to tell us why he/she are not answering question(s).

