1.17 Study Procedure Stopping Criteria

There are no prespecified stopping criteria, as there are no treatment interventions in this study. A participant may withdraw from the study at any time. The Sponsor will be notified of withdrawal. Data obtained up until withdrawal may be used. A participant may be asked to or the study team may terminate participation if they cannot comply with the procedures outlined in the Protocol.

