4.8. Participant Discontinuation

A participant may voluntarily withdraw from the study for any reason, at any time. A participant may be discontinued from the study in any of the following circumstances:

- Any adverse event (AE) that renders the participant ineligible or in the opinion of the principal investigator (PI), makes it not in the best interest of the participant to continue participation.
- After enrollment, if a participant does not meet the inclusion/exclusion criteria of the study (either newly developed or not previously recognized).
- Protocol violation that renders data to be unusable or of questionable accuracy, in accordance with the Data Management and Quality Plan.
- Lost-to-follow up; unable to contact participant.
- Termination of the study by the PI or Sponsor.
- Withdrawal of consent: a research participant may withdraw from participation for any reason at any time.
- Loss of two study-provided devices (smartphone and/or wireless headphone(s) or case).
- PI discretion.

A participant who develops active ear disease (e.g., otitis media; otitis externa; acute tinnitus), even if unilateral, may be withdrawn per PI discretion from participation.

If a participant reports loud environmental sound exposure (e.g., concert; construction site; fireworks) during participation, this should be recorded as it may contextualize setting changes by the participant.

The PI or designee(s) will advise the discontinuation of any participant. Participants who discontinue or are discontinued should be compensated for the study visits they have completed, according to the compensation information in the Informed Consent Form (ICF).

In the event of a participant withdrawal, coded participant data that was previously recorded may be retained and used in accordance with the protocol and ICF. Participants who withdraw from the study must return certain study equipment and materials.

The reason for participant withdrawal from the study will be documented in the relevant tracking database(s). The PI or designee(s) will inform the participant of the reason for withdrawal, as well as recommend steps for seeking additional care from their physician, when applicable.

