7.3.4. Anticipated Adverse Device Effects

There are no Anticipated Adverse Device Effects from the provided smartphone or wireless headphones.

The following occurrences are not to be regarded as AEs:

- Hearing symptoms or diseases (including tinnitus)
- Cerumen impaction
- Abnormal audiogram findings
- Complaint about smartphone or comfort of headphones
- Discomfort or injury with ear exams and/or with removal of ear wax
- Study app functionality issues

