8.1.4.7. International Outcomes Inventory for Hearing Aids (IOI-HA) Survey

This survey will be administered at Clinic Visit 3 and results recorded as primary outcome.

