6.1. Primary Study Endpoints

The primary endpoint for the study is:

- IOI-HA Clinic Visit 3 scores. The average total IOI-HA scores will be compared between the Self-Fit Group and Pro-Fit Group

The International Outcome Inventory for Hearing Aids (IOI-HA) is a seven-item validated questionnaire designed to be generally applicable in evaluating the effectiveness of hearing aid treatments. The inventory was developed to facilitate cooperation among researchers and program evaluators in diverse settings. The survey has seven items assessing (1) daily hearing-aid use, (2) benefit, (3) residual activity limitation, (4) satisfaction, (5) residual participant restriction, (6) impact (of hearing impairment) on others, and (7) quality of life. Each of the 7 items are scored on a 1 (poorest) – 5 (best) Likert scale and summed to obtain a total outcome score ranging from 5 to 35 where higher scores are better.

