7.6. Interim Analyses

There are no interim analyses planned in this study.

8. Analysis Sets

The following analysis sets are defined for this study.

Eligible Analysis Set: All subjects who sign informed consent and meet eligibility criteria for the CV portion of the study. Some of these subjects may not have been randomized if the hearing loss recruitment category is already filled.

Full Analysis Set (FAS): All subjects who sign informed consent, meet eligibility criteria, and are enrolled and randomized into the CV portion of the study. This analysis set will be used for the primary endpoint analysis and to summarize subject accountability, protocol deviations, demographic and baseline characteristics, and adverse event data. Subjects in this analysis set will be analyzed “as randomized”.

Per Protocol Analysis Set (PPS): All subjects who meet predetermined minimum data usability criteria, and who do not have any major protocol deviations that would necessitate exclusion from analysis. Subjects in this analysis set will be analyzed “as treated”. This analysis set will be used as a supportive analysis of the primary endpoint. Subjects in the PP analysis set must meet the following two minimum usability criteria:

- 1) >10 minutes of Airpod wear for at least 1 day during home interval 1 AND
- 2) >10 minutes/day of Airpod wear for at least 7 days during home interval 2

The minimum wear times are justified to obtain the most accurate assessment of hearing aid benefit as measured by the IOI-HA questionnaire.

Complete Cases Analysis Set (CCAS): All subjects who have complete data for the efficacy endpoints of IOI-HA, QuickSIN, or Real Ear Measures. This analysis set will be used as a supportive analysis of the primary endpoint.

9. Analysis Approach

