9.1. Subject Accountability

A summary of the number of eligible subjects, randomized subjects, withdrawn subjects, and completers will be presented by randomized treatment group (if applicable) and overall. Reasons for withdrawal will be summarized according to the following categories:

- Adverse Event
- Loss of Study Provided Materials
- Protocol Violation
- Does Not Meet Inclusion Exclusion Criteria After Enrollment

- Withdrawal of Consent by Subject
- PI Discretion
- Termination of Study
- Lost to Follow-up
- Other

Results of the perceived hearing loss questionnaire will also be summarized descriptively.

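### Participants who cannot wear the headphones are withdrawn with the primary score missing by rule, and the planned analysis fills the gap from those who kept wearing them

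*Protocol*

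**What the plan says.** Under discomfort with headphone wear, Protocol 7.1 states: "If comfort prohibits a participant from this wireless headphone wear, they will be withdrawn from the study". The wording is mandatory and makes stopping wear the same event as leaving the study.

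Protocol 8.1.4.7 fixes the timing of the survey: "This survey will be administered at Clinic Visit 3 and results recorded as primary outcome". SAP 6.1 names the primary endpoint as "IOI-HA Clinic Visit 3 scores". No visit description in Protocol 3.2 or SAP 5 gives the survey at any other time, and neither text describes an early-termination visit or exit survey. (The assessment diagrams are not reproduced in the copies reviewed.) Protocol 1.17 says "Data obtained up until withdrawal may be used", but before Visit 3 there is no primary score to use.

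SAP 8 defines the Full Analysis Set as "All subjects who sign informed consent, meet eligibility criteria, and are enrolled and randomized into the CV portion of the study", analysed as randomised. SAP 9.5 assumes missing Visit 3 scores are missing at random. It screens treatment group and baseline factors for association with missingness and estimates the arm difference by full information maximum likelihood (FIML).

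On visibility, Protocol 7.3.4 lists among occurrences that are not adverse events: "Complaint about smartphone or comfort of headphones". SAP 9.1 says "Reasons for withdrawal will be summarized according to the following categories"; the list has no line for discomfort.

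Three protocol statements do not fit together. Section 7.1 requires withdrawal for discomfort. Section 4.8 lists circumstances in which a participant may be discontinued, without naming discomfort. Section 1.17 says no stopping criteria are prespecified.

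**The concern.** The IOI-HA asks about daily use, benefit and satisfaction (SAP 6.1). Someone who could not wear the device would plausibly score low on these items, yet that is the person whose score is never collected. Being unable to wear the headphones is a post-randomisation event related to the outcome, and the missing-data model contains nothing measured after baseline: no wear time, comfort or reason for withdrawal.

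The supportive analyses do not help. The per-protocol set requires minimum wear in both home intervals, and the complete-cases analysis requires an observed IOI-HA. No missing-not-at-random or tipping-point analysis is planned.

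At stake is the only confirmatory test in the study. Both arms wear the same headphones, but the amplification settings come from different fitters, and Protocol 3.2 itself links settings to discomfort by letting participants adjust them to avoid it. A difference in stopping between arms is therefore possible. If it occurs, later analysis can only assume the scores that a short survey would have recorded.

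**Working it through.** **Inputs from the documents.** Margin 3 points for Pro-Fit minus Self-Fit, and published mean IOI-HA of 25.5 to 28.9 (SAP 6.3). Non-inferiority is declared if the estimate + 1.96 SE is at most 3 (SAP 9.5). 112 participants, 56 per arm (SAP 7.1). At least 90 usable data sets (Protocol 4.2), so the plan tolerates 1 − 90/112 = 19.6% loss from all causes.

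**The plan's own figure.** The SD and power behind 112 are redacted, so it cannot be rebuilt.

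**Assumptions.** Wearers' mean 27, SD 5; stoppers score 14 or 18, SD 4; stopping rates as shown. None of the stopper scores, SDs or stopping rates is in the documents.

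**Step 1: what FIML does with these participants.** With no baseline predictor of missingness and complete baseline data, SAP 9.5 itself says the estimate is the arithmetic mean difference. A numerical check gave 0.439 both from FIML and from observed cases. Withdrawn participants then add nothing to the estimate. With baseline predictors, they are in effect assigned the expected score of similar participants in their arm who have one.

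**Step 2: points per stopper.** With equal wearers' means, each extra Self-Fit stopper hides (27 − 14)/56 = 0.23 points, or (27 − 18)/56 = 0.16. Five hide 5 × 13/56 = 1.2 or 5 × 9/56 = 0.8 points. With equal stopping and equal scores, the shift is 0.

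**Step 3: false non-inferiority.** Set the all-randomised difference exactly at 3. The difference among wearers, δ, follows from the mixture of wearers and stoppers. Then

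P = Φ((3 − δ)/SE − 1.96), with SE = 5 × √(1/n_PF + 1/n_SF), where each n is 56 × (1 − stopping rate).

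Worked case, 15% Self-Fit and 5% Pro-Fit stopping, score 14:
- Pro-Fit overall: 0.95 × 27 + 0.05 × 14 = 26.35, so Self-Fit overall is 23.35.
- Self-Fit wearers: (23.35 − 0.15 × 14)/0.85 = 25.0, so δ = 2.0.
- SE = 5 × √(1/53.2 + 1/47.6) = 0.998.
- P = Φ(1.0/0.998 − 1.96) = 17%.

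| Self-Fit vs Pro-Fit stopping | Stopper score | δ | SE | P |
|---|---|---|---|---|
| 10% vs 5% | 14 | 2.61 | 0.983 | 5.9% |
| 15% vs 5% | 18 | 2.47 | 0.998 | 7.7% |
| 15% vs 5% | 14 | 2.00 | 0.998 | 17% |
| 20% vs 5% | 14 | 1.31 | 1.014 | 38% |
| 10% vs 10% | 14 | 3.33 | 0.996 | 1.1% |
| 5% vs 15% | 14 | 4.53 | 0.998 | under 0.1% |

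Simulation agrees: about 6%, 8%, 17–18%, 38–39%, 1% and under 0.1%. The nominal level is 2.5%. With stoppers' scores collected and used, simulation gave 2.4–3.0% in the scenarios with excess Self-Fit stopping.

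**Step 4: price of using the scores.** With stopping rate w and stopper score s, the variance is (1 − w) × 25 + w × 16 + w(1 − w)(27 − s)². Power is at a true difference of 0.

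| w per arm | s | Variance | Rise over 25 | Power, wearers only | Power, all 56 per arm |
|---|---|---|---|---|---|
| 10% | 18 | 31.4 | 26% | 85% | 81% |
| 10% | 14 | 39.3 | 57% | 85% | 72% |
| 15% | 14 | 45.2 | 81% | 83% | 66% |

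**The case against.** **Nobody is removed from the analysis set.** A reader might infer that the worst outcomes are excluded from the primary analysis. SAP 8 and 9.5 keep every randomised participant, as randomised. This stands: the fault is a score missing by rule plus an optimistic missing-data assumption.

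**The documents do not show a difference between arms.** Section 7.1 concerns headphone comfort, and both arms get the same headphones. Both are taught to change settings at home (Protocol 5.2.3). Unsuitable ear anatomy and unwillingness to wear the headphones are exclusions (Protocol 4.4), which should keep cases few. A reader might infer that the design favours non-inferiority. The documents do not support that: excess Pro-Fit stopping biases against non-inferiority, and equal stopping gave no inflation in the case computed. What remains is that the direction cannot be checked afterwards without the scores.

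**Using the scores has a real price.** The power loss in Step 4 is not slight, and some scores would reflect very short use. Equal stopping can also dilute a true difference: 3.3 points among wearers becomes 0.9 × 3.3 = 2.97 overall at 10% stopping, inside the margin. SAP 8 treats minimum wear as needed for an accurate IOI-HA. This stands, and is why the added analysis belongs beside the planned one.

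**The withdrawals are not invisible.** Protocol 4.8 requires reasons to be documented; the SAP has an Other category, listings of discontinued participants and disposition, and wear time by arm. The missing line in SAP 9.1 is minor.

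**Equipment return is not a visit.** Section 4.8 says "Participants who withdraw from the study must return certain study equipment and materials" but does not require attendance. This also stands, so a remote option is needed.

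**Conclusion.** The point holds as a gap in data collection. By rule, a participant whose comfort prohibits wear has no primary score; the main analysis then treats that participant like similar wearers in the same arm, and neither supportive analysis recovers the outcome. That such people would score low is an inference from the questionnaire's content, though a reasonable one.

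The consequence for the arm comparison is conditional. It needs stopping rates, or stoppers' scores, that differ between arms. With Self-Fit losing 5 to 15 percentage points more, the assumed inputs put false non-inferiority at about 6% to 39%; with equal 10% stopping (score 14) it is about 1%, and with the pattern reversed it is under 0.1%. These are illustrations, not predictions. They do not support a claim that the trial is biased toward its desired result.

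This is a change that should be made because it is cheap and cannot be replaced later. It is not a defect that by itself invalidates the primary analysis.

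**What to change.** 1. **Collect the score.** Without changing any rule on stopping wear, ask every randomised participant who stops wear or is discontinued, and has not withdrawn consent, to complete the IOI-HA at equipment return or remotely in the Visit 3 window. Record the date and the wear time up to then.
2. **Use it.** Prespecify in SAP 9.5 a Full Analysis Set analysis, as randomised, that includes these scores and is reported beside the missing-at-random analysis.
3. **Show it.** Add headphone discomfort or intolerance to the withdrawal reasons in SAP 9.1, tabulated by arm.
4. **Reconcile the text.** Protocol 7.1, 4.8 and 1.17 must be brought into agreement on withdrawal for discomfort. Which rule should apply is for the sponsor and investigators.

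Cost: protocol and SAP wording and a seven-item survey, with no added visit if the remote route is used. Some scores will reflect short use. In the added analysis, variance rises by about 26% to 81% under the assumptions above, and power falls, for example from 85% to 72% with 10% stopping per arm and a stopper score of 14.
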